3.3. Benefit/Risk Assessment

More detailed information about the known and expected benefits, risks and reasonably expected adverse events of GSK3772847 may be found in the IB (GlaxoSmithKline Document Number 2017N316832 00).

	investigational product. No specific cause was identified. Data on this event was reviewed by GSK (Internal Cardiac Safety Panel and CMO), and was not considered to impact further clinical development.	
	During 12 hours post-dose telemetry monitoring in Part 1 of Janssen study CNTO7160ASH1001, 6 out of 60 completed subjects were assessed to have abnormal findings by the investigator. The abnormalities were considered clinically significant and recorded as treatment emergent adverse events.	
	In Part 2 of the Janssen study CNTO7160ASH1001, there were four reports of non-sustained ventricular tachycardia. Of these reports, one participant received placebo and two received GSK3772847 at 3 mg/kg and one received GSK3772847 at 10 mg/kg. The events were non-symptomatic, and a monomorphic pattern (i.e., not Torsades de pointes), which is a	
	pattern (i.e., not forsades de pointes), which is a pattern thought not to be indicative of increased risk for sudden ventricular tachycardia and sudden death. Heart rate (HR) analysis did not identify any safety concern (no pattern of increased HR suggestive of an increase in sympathetic tone). All 4 participants had normal results from exercise test and echocardiogram.	

Potential Risk of Clinical Significance	Summary of Data/Rationale for Risk	Mitigation Strategy
	Dosing was continued as planned, and the dose escalated to 10 mg/kg.	
Increased risk of infections & immunosuppression Studies in mice indicate a potential role for IL-33 in infection control. IL-33 was shown to activate neutrophils in BALB/c mice subjected to cecal ligation and puncture thus preventing polymicrobial sepsis. Similarly, IL-33 is thought to stimulate neutrophil recruitment from the bone marrow to the periphery in response to fungal infection. Mice infected with flu virus and administered an IL-33 inhibitor exhibited a lower number of clusters of differentiated CD90+ and cluster of differentiated CD25+ inate lymphoid cells with consequent impaired lung function compared to phosphate buffered saline treated controls. IL-33 has also been shown to be produced in the helminth infected cecum of parasite infected mice and is shown to be important in expulsion of the parasite.	Preclinical: No GSK3772847-related changes in clinical signs, white blood cell count or no microscopic changes (inflammatory cell infiltrates) in any tissues indicative of infection observed in monkey 4 week IV/SC or IV 3 month toxicity at doses ≤100 mg/kg/week. Clinical: Safety data from Janssen study CNTO7160ASH1001 Single Ascending Dose (SAD) has shown the most frequent adverse events reported as infections, including nasopharyngitis, rhinitis, gastroenteritis and upper respiratory tract infection. The frequency of these events was similar in GSK3772847 and placebo groups (18/45 [40%] of participants administered GSK3772847 versus 6/24 [40%] administered placebo). Safety data from Part 2 of the Janssen study CNTO7160ASH1001 have shown the Systemorgan class (SOC) with the most frequent adverse events reported was 'Infections and infestations'. The number of asthma participants experiencing infections and infestations was	Participants with a known, pre-existing parasitic infestation within 6 months prior to Screening are excluded from participation in the study (Section 6.2) Participants who develop an infection will be requested to seek medical advice, and subject to close monitoring. EU Regulatory guidance on development of asthma drugs request that agents that interact with the immune system should be investigated for their effect on the host response to infection and tumours. The incidence of infections will be monitored in clinical studies. Incidence of tumours and development of paradoxical immune responses (e.g. idiopathic thrombocytopenic purpura, autoimmune thyroiditis, multiple sclerosis-like syndrome) will be monitored in clinical trials and routinely as part of the post marketing pharmacovigilance process. Exclude patients with ongoing or recurrent infections.

Potential Risk of Clinical Significance	Summary of Data/Rationale for Risk	Mitigation Strategy
	similar between the group receiving GSK3772847 (9/18 [50%]) and the group receiving placebo (4/6 [66.7%]). The frequency of infection events in participants with atopic dermatitis was greater in participants in the GSK3772847 group compared with the placebo group (6/11 [54.5%] versus 1/4 [25%]). The most frequently-reported infection was nasopharyngitis	Close monitoring of infection AEs (including pneumonia).
Increased risk of hyper-sensitivity, anaphylaxis, cytokine release syndrome (CRS) Therapy with other mAbs has been associated with hypersensitivity reactions which may vary in severity and time of onset.	Not observed in studies to date. Clinical: Not observed in Janssen study CNTO7160ASH1001 in healthy volunteers following single doses up to 10 mg/kg, and multiple doses in asthma and atopic dermatitis patients at doses up to 10 mg/kg (3 doses, once every two weeks [q2W] over four weeks). Based on in vitro cytokine release data and safety experience in Janssen study CNTO7160ASH1001 the risk of CRS is considered negligible.	If a hypersensitivity or anaphylactic reaction occurs, infusion should be discontinued immediately and appropriate therapy instituted. Agents to treat reactions should be available immediately. Stopping & continuation criteria will be included in protocols. Painkillers can be prescribed for pain at site of injection. Patients developing hypersensitivity, anaphylactic reactions or anaphylactic shock will be withdrawn from the study. All doses in this trial will be administered in the clinic.
Possible interaction with live virus or bacterial vaccines	Non-clinical: In the monkey 13 week toxicity study no	In the study, participants should not be vaccinated with live or attenuated vaccines within
As GSK3772847 is an immunomodulator, there is a possibility that the subject will not mount an adequate immune response to a vaccine or even	GSK3772847-related changes in the T cell dependent B cell response (IgM or IgG) was observed at doses ≤ 100 mg/kg/week. This data is indicative that healthy monkeys were able to	4 weeks prior to receiving IP or up to 6 months after dose administration of GSK3772847. However, vaccines containing killed bacteria or inactivated virus will be permitted.

Potential Risk of Clinical Significance	Summary of Data/Rationale for Risk	Mitigation Strategy
cause the infection the vaccine should protect against. Steroid withdrawal is expected to augment a proinflammatory response in the lung of the patients that drives the asthma phenotype. Vaccination will also drive a systemic immune response to the pathogen antigen that runs the risk of causing some immunomodulation of the lung immune responses. This has been best studied in murine models where eosinophilic lung inflammation has been suppressed by systemic toll-like receptor activation.	mount a response against the antigen challenge during GSK3772847 administration at doses where near complete inhibition of IL-33 was anticipated. Based on this data GSK3772847 is considered unlikely to blunt/inhibit the generation of a response to vaccinations. Clinical: Not observed in Janssen study CNTO7160ASH1001 in healthy volunteers following single doses up to 10 mg/kg, and multiple doses in asthma and atopic dermatitis patients at doses up to 10 mg/kg (3 doses, once	
	every two weeks over four weeks).	
Gastrointestinal disordersNauseaVomiting	Clinical: In Part 2 of Janssen study CNTO7160ASH1001, the incidence of gastrointestinal disorders was greater in participants in the GSK3772847 groups compared with the placebo groups: 6/18 (33.3%) participants in the asthma cohort and 3/11 (27.3) participants in the atopic dermatitis cohort as compared with 0 participants in either the asthma cohort or atopic dermatitis cohort placebo groups. Gastrointestinal disorders events included nausea (1/18 participants in the asthma cohort, 2/11 participants in the atopic dermatitis cohort), vomiting, diarrhoea.	The incidence and severity of nausea and vomiting will be monitored.

Potential Risk of Clinical Significance	Summary of Data/Rationale for Risk	Mitigation Strategy
Skin and subcutaneous tissue disorders • Contact dermatitis	Clinical: In Part 2 of Janssen study CNTO7160ASH1001, the incidence of contact dermatitis was greater in participants in the GSK3772847 groups compared with the placebo groups. In the asthma cohort, the number of participants with contact dermatitis was 4/18 (22.2%) in the combined GSK3772847 groups versus 1/6 (16.7%) in the placebo group. In the atopic dermatitis, the number of participants with contact dermatitis was 3/11 (27.3%) in the combined GSK3772847 versus 0/4 (0%) in the placebo group.	The incidence and severity of contact dermatitis will be monitored.

3.3.2. Benefit Assessment

Efficacy of GSK3772847 has not yet been demonstrated and there are no existent data from molecules with the same or similar mode of action. Taking part in this study may or may not improve a participant's health, and may or may not directly benefit a participant. This study will provide additional safety and efficacy information on GSK3772847.

Whilst the *in vivo* models of T2 asthma support a role for IL-33 pathway in eosinophilic asthma disease, it is clear that IL-33 plays a significant role in other types of immune responses and cell types including amplification of Th1 and Th17 responses in combination with other cytokines [Arshad, 2016; Smithgall, 2008]. Agents targeting this mechanism could be expected to have effects on both type 2 (T2)-driven and non-T2-driven disease. Currently available marketed biological treatments for the treatment of severe asthma are indicated for patients with T2-driven disease, refractory eosinophilic asthma, or patients with IgE-mediated asthma. There is currently no marketed treatment for non T2-driven severe asthma.

All study participants will receive open label salbutamol/albuterol to use as needed for asthma symptom relief from Screening to the end of the Treatment Period. Medical assessments are planned during the study to evaluate participants' health status. The assessments include physical examination, vital signs, electrocardiogram (ECG), Holter monitoring, and clinical laboratory evaluation including liver chemistry and blood chemistry panel at a number of clinic visits.

Participants will be monitored for changes in asthma control through daily use of an electronic Diary (eDiary) and twice-daily PEF measurements. The participants will use the eDiary to record asthma symptoms, rescue medication use, and nocturnal awakening due to asthma symptoms requiring rescue medication use. Alerts, indicative of worsening asthma, will be programmed into the eDiary with instructions for the participant to contact the investigator and send the data as soon as possible. Data will also be transmitted automatically within 24 hours to the centralised server. Email notifications will be sent to the investigator as soon as the data is transmitted to the centralized server allowing the investigator to contact the participants in order to discuss the participants' symptoms and evaluate whether they experienced loss of asthma control. Participants' health status will also be evaluated by ACQ-5 and SGRQ during the study. With this built-in safety monitoring and the frequent visit schedule, a participant will be withdrawn from study treatment due to experiencing symptomatic or spirometric changes that meet one of the pre-defined loss of asthma control criteria and will be started on alternative standard of care therapy. The aim will be to retain participants in the study post withdrawal of study medication to follow-up for safety.

Potential participants must be clinically stable on their asthma regimen for at least 4 months prior to study entry. The Global Initiative for Asthma (GINA), 2016 Guidelines advocate attempting to discontinue LABA if possible and step-down therapy once adequate asthma control is met. During ICS titration, the lowest effective dose is determined at the dose, below which asthma control deteriorates. According to GINA 2016 Guidelines, during this process the patients' asthma status is closely monitored and a clear plan is provided to the patients with instructions on how asthma symptoms should

be documented by the patients and the action plan that should be followed if previous therapy needs to be resumed. Similarly, in this study, participants will have their asthma status documented at study entry, their symptoms and PEF will be monitored twice daily, scheduled visits will be arranged and they will have clear instructions as to what actions to take with any increase in asthma symptoms. Furthermore, a potential benefit to the subjects would be the ascertainment that asthma control might be maintained on a lower ICS dose than that which the subject received prior to study entry, with the potential for fewer or less severe ICS-related adverse events.

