5.4. Scientific Rationale for Study Design

This study will use a multicenter, randomized, double-blind, parallel-group and placebo-controlled design. This is a well-established design to evaluate the efficacy, safety, PK and PD profiles of an investigational drug. The design of steroid titration (oral or inhaled) in participants with asthma has been used in various studies with different investigational products, in which changes in the level of asthma control were induced by medication withdrawal [Bel, 2014; Wenzel, 2013; Nair, 2009]. This design may not reflect real world fluctuations in asthma control, however studies with the design of steroid titration have shown the ability to assess effects of a potential treatment on changes in asthma control in a relatively short period of time, before further investigations are conducted in longer term studies.

In this study, the target population would be participants with moderately severe asthma and with an ACQ5 score ≥1 and <4 whose symptoms must have been managed on a stable, high dose ICS/LABA for at least 4 months prior to Screening. The use of loss of asthma control as a composite study endpoint and a criterion for ICS titration allows for the overall clinical evaluation of the participant's asthma status taking into account both lung function and symptom control. Participants will also be monitored through the use of the eDiary. Pre-specified asthma symptom scores and participant-measured PEF that is inputted into the eDiary will be used as prompts for contacts between subjects and investigators (Section 9.1.2.3).

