6.1. Inclusion Criteria

Participants are eligible to be included in the study only if all of the following criteria apply:

- 1. **Age:** At least 18 years of age at the time of signing the informed consent.
- 2. **Gender**: Males and females.

A female participant is eligible to participate if she is not pregnant (see Appendix 5), not breastfeeding, and at least one of the following conditions applies:

- Not a woman of childbearing potential (WOCBP) as defined in Appendix 5.
- i. OR
- A WOCBP who agrees to follow one of the options listed in Appendix 5 from 4 weeks prior to the first dose of study medication and until at least 16 weeks after the last dose of study medication and completion of the follow-up visit.
- 3. **Informed consent**: Capable of giving signed informed consent which includes compliance with the requirements and restrictions listed in the consent form and in this protocol.
- 4. **Asthma diagnosis and severity**: A participant with a documented diagnosis of moderate-severe asthma based on Global Initiative for Asthma (GINA), 2016 Guidelines, whose asthma has been managed with regular treatment of high dose ICS defined as fluticasone propionate 500 mcg twice daily (i.e. 1000 mcg total daily dose) or equivalent, and long-acting beta-2-agonist (LABA) for at least 4 months. Additional therapy with a leukotriene receptor antagonist (LTRA) is permissible.
- 5. **Reversibility:** Airway reversibility of at least 12 % and 200 mL in FEV1 at Screening (Visit 1), or documented reversibility prior to Screening (Visit 1), or documented history of bronchial hyperreactivity (e.g. fall in FEV1 from baseline of

 $\geq 20\%$ with standard doses of methacholine or histamine, or $\geq 15\%$ with standardized hyperventilation, hypertonic saline or mannitol challenge) from a bronchoprovocation study (e.g. methacholine challenge) prior to Screening (Visit 1).

CONFIDENTIAL

Note: If the participant does not meet the above reversibility criteria at Screening (Visit 1) then the reversibility assessment may be repeated once within 7 days of Visit 1. Should the participant successfully demonstrate airway reversibility at the second attempt then, provided that all other eligibility criteria assessed at Screening (Visit 1) are met, the participant may enter the 2-week run-in period.

- 6. Asthma Control Questionnaire (ACQ): ACQ-5 score ≥ 1 and ≤ 4 at Screening (Visit 1).

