- 7. **Exacerbation history**: Had at least one asthma exacerbation within 12 months prior to Screening that required treatment with systemic corticosteroid and/or hospitalization.
- 8. Short-Acting Beta2-Agonists: All subjects must be able to replace their current SABA treatment with albuterol/salbutamol aerosol inhaler at Visit 1 for use as needed, per product label, for the duration of the study.

6.2. **Exclusion Criteria**

Participants are excluded from the study if any of the following criteria apply:

- 1. Smoking history: Current smokers or former smokers with a smoking history ≥ 10 pack years.
- 2. Concurrent respiratory diseases: Presence of a known pre-existing, clinically important respiratory conditions (e.g. pneumonia, pneumothorax, atelectasissegmental or larger, pulmonary fibrotic disease, bronchopulmonary dysplasia, chronic bronchitis, emphysema, chronic obstructive pulmonary disease, or other respiratory abnormalities) other than asthma.
- 3. Severe airflow obstruction: A pre-bronchodilator FEV1 <50 % predicted of normal value at Screening (Visit 1). Predicted values will be based upon Global Lung Function Initiative (GLI) [Quanjer, 2012] equations for spirometry reference values.
 - Note: If the spirometry is deemed technically inadequate by the central reader, the spirometry assessment may be repeated once within 7 days of Screening (Visit 1).
- 4. Malignancy: Participants with a diagnosis of malignancy or in the process of investigation for a malignancy. Participants with carcinoma that have not been in complete remission for at least 5 years. Participants who have had carcinoma in situ of the cervix, squamous cell carcinoma and basal cell carcinoma of the skin would not be excluded based on the 5 year waiting period if the patient has been considered cured by treatment.
- 5. Presence of hepatitis B surface antigen (HBsAg), positive hepatitis C antibody test result at Screening (Visit 1) or within 3 months prior to first dose of study treatment.

- NOTE: Participants with positive Hepatitis C antibody due to prior resolved disease can be enrolled, only if a confirmatory negative Hepatitis C Ribonucleic acid (RNA) test is obtained.

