- syndrome or bifascicular block defined as complete left bundle branch block or complete right bundle branch block with concomitant left fascicular block)
- Clinically significant arrhythmias (e.g., atrial fibrillation with rapid ventricular response, ventricular tachycardia)
- 7. **Weight**: <50 kg and > 150 kg
- 8. **Regular use of systemic corticosteroids** for conditions including asthma within 3 months prior to Screening (Visit 1).
- 9. **Participants with high parasympathetic tone** (e.g. trained athletes with baseline bradycardia) or chronic conditions associated with parasympathetic surges (e.g. migraines)
- 10. **Eosinophilic diseases**: Other conditions that could lead to elevated eosinophils such as hypereosinophilic syndromes. Participants with a known, pre-existing parasitic infestation within 6 months prior to Screening (Visit 1).
- 11. **Cardiovascular disease**: Clinically significant organic heart disease (e.g. CAD, NYHA Class III/IV heart failure).
- 12. **Ongoing infections** (i.e. not resolved within 7 days prior to Screening [Visit 1]) or recurrent infections (i.e. requiring treatment for an identical diagnosis within 3 months) requiring systemic antibiotics. Known, pre-existing parasitic infestations within 6 months prior to Screening.
- 13. Other Concurrent Diseases/Abnormalities: A subject must not have any clinically significant, uncontrolled condition, or disease state that, in the opinion of the investigator, would put the safety of the subject at risk through study participation or would confound the interpretation of the efficacy results if the condition/disease exacerbated during the study.

The list of additional excluded conditions/diseases includes, but is not limited to, the following:

Addison's disease	hypertension ¹ (uncontrolled)	
aortic aneurysm (clinically significant)	peptic ulcer (recent or poorly controlled)	
Cushing's disease	renal disease	
diabetes mellitus (uncontrolled)	stroke within 3 months of Visit 1	
hematological disease	thyroid disorder (uncontrolled)	
hepatic disease	tuberculosis (current or untreated ²)	

- 1. Two or more measurements with systolic pressure >160mmHg or diastolic pressure >100mmHg
- 2. Subjects with a history of tuberculosis infection who have completed an appropriate course of antituberculosis treatment may be suitable for study entry provided that there is no clinical suspicion of active or recurrent disease.

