- 14. **Immunodeficiency**: A known immunodeficiency such as human immunodeficiency virus infection
- 15. **Hypersensitivity**: Participants with allergy or intolerance to a monoclonal antibody or biologic or to any components of the formulation used in this study.

- 16. **Alcohol and Substance abuse**: Participants with a history (or suspected history) of alcohol misuse or substance abuse within 2 years prior to Screening (Visit 1).
- 17. Participants at risk of non-compliance, or unable to comply with the study procedures. Participants who are unable to follow study instructions such as visit schedule, dosing directions, study eDiary completion, or use of a standard metered dose inhaler. Participants who have known evidence of lack of adherence to controller medication and/or ability to follow physician's recommendations. Any infirmity, disability, or geographic location that would limit compliance for scheduled visits.
- 18. Participants who have previously participated in a study of GSK3772847.
- 19. **Excluded Medications**: Use of the medications listed in Table 3 is not permitted within the defined time intervals prior to Screening (Visit 1) and throughout the study. Potential participants should not be washed out of their medication solely for the purpose on enrolling in the trial.

Table 3 Prohibited Medications

2017N311825_02

Medication	Time interval prior to Visit 1
Investigational drug	One month or 5 half-lives whichever is longer
Live or attenuated vaccines ^a	2 weeks (i.e. 4 weeks prior to IP administration)
Biologics, for example Mepolizumab and	130 days or 5 half-lives whichever is longer
Omalizumab	
Experimental anti-inflammatory drugs (non-	3 months
biologics)	
Corticosteroids intramuscular, long acting depot	3 months
Regular systemic corticosteroid - oral,	
parenteral, depot	
Methotrexate, troleandomycin, oral gold,	3 months
cyclosporin, azathioprine,	
Theophylline	3 months
Chemotherapy and radiotherapy	12 months
Inhaled anti-cholinergics e.g. tiotropium	1 week

- a. Vaccines containing killed bacteria or inactivated virus will be permitted
- 20. **Affiliation with Investigator Site**: A participant will not be eligible for this study if he/she is an immediate family member of the participating investigator, sub-investigator, study coordinator, or employee of the participating investigator.

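### Section 6 sets no recovery interval after an exacerbation or short systemic steroid course before background treatment is withdrawn, although Section 3.3.2 leans on 4 months of stability

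*Protocol*

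**What the plan says.** Section 3.3.2 states "Potential participants must be clinically stable on their asthma regimen for at least 4 months prior to study entry". The next sentence cites guideline advice to stop the long-acting beta-agonist (LABA) where possible and to "step-down therapy once adequate asthma control is met". Together they support the withdrawal schedule.

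Section 5.4 describes the same 4 months as symptoms "managed on a stable, high dose ICS/LABA for at least 4 months prior to Screening". Section 6.1 item 4 is the only 4-month entry criterion. It asks for regular high-dose inhaled steroid (ICS), defined as a fluticasone propionate (FP) dose or "equivalent, and long-acting beta-2-agonist (LABA) for at least 4 months".

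On exacerbations and systemic steroids:
- Section 6.1 item 7 requires that the participant "Had at least one asthma exacerbation within 12 months prior to Screening that required treatment with systemic corticosteroid and/or hospitalization". It sets no minimum gap before Screening.
- Section 6.2 item 8 and Table 3 ("Regular systemic corticosteroid - oral" and other routes, plus intramuscular and depot forms), and Section 7.7.2 during the study, do not name a short oral course.
- Section 6.4 item 5 excludes an exacerbation still ongoing at Visit 2. Sections 6.4 and 6.6 allow re-screening from 2 weeks after that visit, with all screening assessments repeated.

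Salmeterol stops at Visit 4 and FP is first reduced at Visit 5 (Section 5.1).

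**The concern.** The stability statement is part of the benefit-risk case for taking participants off LABA and then off ICS. The entry criteria secure time on treatment. They do not secure recovery from a recent event: someone whose exacerbation or oral steroid course ended the day before Visit 2 breaks no listed criterion.

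Two things are at stake. The first is safety: Section 5.4 says the design should make an actual exacerbation less likely. The second is the Visit 2 reference. The FEV1 and ACQ-5 loss-of-control criteria are changes from Visit 2, and the PEF alert is a change from the last 7 Run-in days. If the reference is taken in recovery, these trigger late. If it is taken just after steroids, a return to the usual level can be counted as loss of control.

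**Working it through.** **Timing.** Inputs are the study days and windows in the Schedule of Activities: Visit 2 = Day 1, Visit 4 = Day 15 ±2, Visit 5 = Day 29 ±3.
- Visit 2 to salmeterol withdrawal: 15 − 1 = 14 days, matching the two weeks stated in Section 5.1. With the window, Day 13 to 17 gives 12 to 16 days.
- Visit 2 to first FP cut: 29 − 1 = 28 days. With the window, Day 26 to 32 gives 25 to 31 days.
- For an event ending at Screening, add the 14-day Run-in: 14 + 14 = 28 days to salmeterol withdrawal and 14 + 28 = 42 days to the first FP cut.
- After re-screening at the earliest time: 14 + 14 = 28 days from the failed Visit 2 to the new one, then 28 + 14 = 42 and 28 + 28 = 56 days to the two steps.

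**Shift of the FEV1 criterion.** The documents give no size for the effect of recovery or recent steroids, so the shifts below are assumed. If Visit 2 FEV1 is a fraction d below usual, a fall of more than 7.5% from Visit 2 means a fall from usual of more than 1 − (1 − d) × 0.925.

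| Visit 2 FEV1 below usual | Calculation | Triggers at more than (below usual) |
|---|---|---|
| 0% | 1 − 0.925 | 7.5% |
| 5% | 1 − 0.95 × 0.925 | 12.1% |
| 10% | 1 − 0.90 × 0.925 | 16.8% |
| 15% | 1 − 0.85 × 0.925 | 21.4% |

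In the other direction, if Visit 2 FEV1 is more than 1/0.925 − 1 = 8.1% above usual, a return to usual meets the criterion by itself.

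**Shift of the ACQ-5 criterion.** With Visit 2 ACQ-5 0.5 above usual, a rise of 0.5 + 0.5 = 1.0 over usual is needed. With it 0.5 below usual, a return to usual is enough.

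**How many would a pre-Screening interval touch?** Assume one exacerbation per person, uniformly timed over the 52 weeks before Screening. The expected share in the last w weeks is w/52.
- 2 weeks: 2/52 = 3.8%.
- 4 weeks: 4/52 = 7.7%, and 0.077 × 300 ≈ 23 of the 300 screened.
- 6 weeks: 6/52 = 11.5%.
- Two independent exacerbations, 4 weeks: 1 − (48/52)² = 14.8%, about 44 of 300.

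These are expected values, not bounds. The assumption places the events before Screening, so it says nothing about events in the Run-in.

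**The case against.** The strongest reply is that nothing contradicts: Section 3.3.2 speaks of stability on the regimen, Section 5.4 of a stable ICS/LABA regimen, and Inclusion 4 enforces 4 months of that treatment. This reading is available. A reader might infer that the protocol promises 4 months free of exacerbations and then breaks the promise; the wording does not go that far. What survives is that a stable regimen does not show recovery from a recent event, and that Section 3.3.2 should say which stability it means.

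A reader might also infer that about 23 of 300 face the 14-day gap. They do not. That count is of events in the 4 weeks before Screening, which already leave at least about 28 days to salmeterol withdrawal. The number in the worst case cannot be derived from the documents.

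The safeguards are real, and several do not use the Visit 2 reference: investigator-judged inability to titrate, the oral-steroid or hospitalisation criterion, the symptom-score and awakening alerts, and the floor of 50% predicted FEV1 at Visits 1 and 2. Participants also stay on FP/salmeterol 500/50 through the Run-in and for 2 more weeks, and control is assessed before each FP cut. These lower the risk but do not restore a sound Visit 2 reference.

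The re-screening route is a remote hazard. For the worst case to recur, the exacerbation would have to last about 4 weeks and end just before the new Visit 2.

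Finally, a recovery interval does not make entrants well controlled. Entry requires an ACQ-5 of at least 1, and Section 9.1.1.1 calls 1.5 or more poorly controlled. That is a limit of the remedy, and a reason to reword the rationale as well.

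**Conclusion.** The gap is real but small. Section 6 contains no recovery interval for an exacerbation or short systemic steroid course, so the schedule permits salmeterol withdrawal 14 days, and the first FP cut 28 days, after an event that ended just before Visit 2. Two of the four loss-of-control criteria may then rest on an unrepresentative reference.

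The timing follows from the schedule alone. The threshold shifts and the count of 23 rest on the stated assumptions. A stronger inference, that the treatment comparison is biased, is not supported: eligibility and the reference are fixed before treatment starts and apply equally to both arms. No sample size or power figure is affected. This is a cheap improvement of minor severity.

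**What to change.** 1. Extend Section 6.4 item 5 from an exacerbation ongoing at Visit 2 to any exacerbation or systemic corticosteroid course during the Run-in. This removes the worst case.
2. Add to Section 6.2 a short fixed interval before Visit 1, for example 4 weeks, free of any exacerbation or systemic corticosteroid course, short courses included. The length is a clinical choice; the documents supply no figure. Allow re-screening in Section 6.6 for those who fail item 1 or 2. The interval then also applies at re-screening.
3. Reword Section 3.3.2 to what is enforced: 4 months on the high-dose ICS/LABA regimen plus this interval.

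A 4-month exacerbation-free period is not needed, and Inclusion 7 stays, so exacerbation-prone participants are still selected.

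The cost is eligibility wording and one sentence. Section 7.7 already records asthma medication from about 12 weeks before screening, and Section 9.2 records exacerbations from screening. Under the one-event assumption, about 23 of 300 screened would wait up to about 4 weeks; with two events, about 44. Those failing item 1 would also repeat the Run-in, in a number that cannot be estimated here. If Section 6.6 is not changed, those failing item 2 are lost rather than delayed, and keeping the same yield would take about 300/(1 − 4/52) = 325 screened, or 300/(48/52)² = 352 with two events.
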